**Table 1-1 Study Medications**

Stratum	Study Medications	
	LCZ696	IMT
ACEi	LCZ696 Active + Enalapril Placebo	LCZ696 Placebo + Enalapril Active
ARB	LCZ696 Active + Valsartan Placebo	LCZ696 Placebo + Valsartan Active
No RASi	LCZ696 Active	LCZ696 Placebo

No interim analysis (IA) for efficacy is planned.

## 1.2 Study objectives and endpoints

[Table 1-2](#) presents the objectives and related endpoints

**Table 1-2 Objectives and related endpoints**

Objective(s)	Endpoint(s)

Primary Objective(s)
 
 
To demonstrate that LCZ696 is superior to IMT for comorbidities in reducing NT-proBNP from baseline after 12 weeks of treatment
 
To demonstrate that LCZ696 is superior to IMT for comorbidities in improving exercise capacity as assessed by the six-minute walk test (6MWT) at Week 24 in a subset of patients
 
	
Endpoint(s) for primary objective(s)
 
 
Change from baseline in NT-proBNP (in log scale) at Week 12
 
Change from baseline in six-minute walk distance (6MWD) at Week 24
 

Secondary Objective(s)
 
 
To compare LCZ696 to IMT for comorbidities on mean change of Kansas City Cardiomyopathy Questionnaire (KCCQ) clinical summary score (CSS) at Week 24
 
To compare LCZ696 to IMT for comorbidities on proportion of patients with <math>\geq 5</math>-points change in KCCQ CSS at Week 24 (separate analyses for <math>\geq 5</math>-points improvement and <math>\geq 5</math>-points deterioration)
 
To compare LCZ696 to IMT for comorbidities in improving NYHA functional class at Week 24
 
To compare LCZ696 to IMT for comorbidities in improving symptoms as assessed by the Short Form Health Survey (SF-36) physical component summary (PCS) score at Week 24
 
	
Endpoint(s) for secondary objective(s)
 
 
Mean change from baseline in KCCQ CSS at Week 24
 
Proportion of patients with <math>\geq 5</math>-points deterioration in KCCQ CSS at Week 24
 
Proportion of patients with <math>\geq 5</math>-points improvement in KCCQ CSS at Week 24
 
Change from baseline in NYHA functional class at Week 24
 
Change from baseline in SF-36 PCS score at Week 24
 

Objective(s)	Endpoint(s)

Exploratory Objective(s)
 
 
• To compare LCZ696 to IMT for comorbidities in reducing NT-proBNP at Week 24
 
• To explore the relative effect of LCZ696 vs IMT for comorbidities on renal function as assessed by estimated glomerular filtration rate (eGFR) at Week 24
 
• To compare LCZ696 to IMT for comorbidities on mean change of KCCQ overall summary score (OSS) at Week 24
 
• To compare LCZ696 to IMT for comorbidities on proportion of patients with <math>\geq 5</math> points change in KCCQ OSS at Week 24 (separate analyses for <math>\geq 5</math>-points improvement and <math>\geq 5</math>-points deterioration)
 
• To evaluate safety of LCZ696 vs IMT for comorbidities
 
	
Endpoint(s) for exploratory objective(s)
 
 
• Change from baseline in NT-proBNP (in log scale) at Week 24
 
• Rate of change (slope) in eGFR from baseline
 
• Mean change from baseline in KCCQ OSS at Week 24
 
• Proportion of patients with <math>\geq 5</math>-points deterioration in KCCQ OSS at Week 24
 
• Proportion of patients with <math>\geq 5</math>-points improvement in KCCQ OSS at Week 24
 
• Frequency of adverse events (AEs), serious adverse events (SAEs), and laboratory abnormalities
 

## 2 Statistical methods

The following section contain important information on detailed statistical methodology used for analysis and reporting purposes.

### 2.1 Data analysis general information

Unless otherwise specified, data will be analyzed by DATAMAP according to the protocol for CLCZ696D2302, using SAS 9.4 or higher. Further details on planned statistical analyses will be presented in the following section and in CSR Appendix 16.1.9.

An established program level data monitoring committee (DMC) independent of Novartis that reviews safety data from LCZ696 studies will be used for this study. The DMC will review patient safety data in an unblinded manner approximately every six months and determine if it is safe to continue the study. Any major recommendation from the DMC will be communicated to the Executive Committee and must be reviewed and ratified by the Executive Committee in consultation with Novartis prior to its enactment.

In general, the continuous variables will be summarized using number of observations, mean, standard deviation, median, quartiles, minimum and maximum; the categorical variables will be summarized using frequencies and percentages.

The analysis will be conducted on all data at the end of trial.

#### 2.1.1 General definitions

##### Randomized Treatment Epoch

The randomized treatment epoch is defined as the period from the date of randomization to the end of the study, inclusive.

## Baseline assessment and study day

Unless otherwise specified, the baseline assessment is defined as below.

- For efficacy variables, if the scheduled assessment at randomization (nominal visit) is performed and the assessment value is non-missing, the baseline assessment is defined as the scheduled assessment at randomization (nominal visit).
- For efficacy variables, if the scheduled assessment at randomization (nominal visit) is not performed or the assessment value is missing, the baseline assessment is defined as the last non-missing assessment (scheduled or unscheduled) prior to or on the randomization date.
- For safety variables, the baseline assessment is defined as the last non-missing assessment (scheduled or unscheduled) prior to or on the first dose date of the study drug.

Specifically, the baseline systolic blood pressure (BSBP) is included in some efficacy analysis model as a covariate, in this case, the baseline assessment for the systolic blood pressure will be defined using the above criteria for efficacy variables.

In the listings, the study day will be displayed, as applicable.

- In the listings of efficacy data, the study day is defined as the date of assessment (event/visit) minus the date of randomization plus one day, i.e., Day 1 is the randomization date.
- In the listings of safety data, the study day is defined as the date of assessment (event/visit) minus the date of first dose plus one day, i.e., Day 1 is the first dose date.

## Post-baseline assessment

Unless otherwise specified, for efficacy variables, the post-baseline assessments are defined as those assessments taken later than the date of randomization; for safety variables, the post-baseline assessments are defined as those assessments taken later than the first dose date of the study drug.

## Region and stratum (ACEi, ARB, No RASi)

Unless otherwise specified, the region and the stratum (ACEi, ARB, No RASi) will be loaded from the randomization data, where the region is defined based on country according to [Table 2-1](#), which may be updated according to the final enrollment plan prior to the database lock, and the stratum is defined based on the usage of the RASi (ACEi/ARB) medication prior to the randomization.

**Table 2-1**      **Region mapping criteria**

Region	Countries
North America	Canada, United States
Latin America (including Central America)	Argentina, Brazil, Colombia, Guatemala, Mexico, Peru
Europe	Austria, Belgium, Bulgaria, Czech Republic, Denmark, Estonia, France, Germany, Hungary, Italy, Latvia, Lithuania, Netherlands, Portugal, Romania, Russia, Serbia, Slovakia (Slovak Republic), Spain, Turkey, United Kingdom

Region	Countries
Asia/Pacific and other	India, Israel, Thailand

## Visit 199 mapping

For patients who completed the randomized treatment epoch, Visit 199 will be Week 24.

For patients who discontinued from the study during the randomized treatment epoch, Visit 199 will be mapped to the next scheduled visit of the last attended scheduled visit prior to visit 199 (Table 2-2).

**Table 2-2 Visit 199 mapping criteria**

Randomized Treatment Epoch Patient Status	Last Attended Scheduled Visit Prior to Visit 199		Mapped Visit for Visit 199	
	Visit Number	Visit Name	Visit Number	Visit Name
Discontinued	101	Randomization	102	Week 2
Discontinued	102	Week 2	103	Week 4
Discontinued	103	Week 4	104	Week 8
Discontinued	104	Week 8	105	Week 12
Discontinued	105	Week 12	106	Week 16
Discontinued	106	Week 16	107	Week 20
Discontinued	107	Week 20	108	Week 24
Completed	---	---	108	Week 24

- For each patient, the last attended scheduled visit prior to visit 199 is defined as the visit with maximal visit number among all scheduled visit ( visit 101 to visit 107) in the visit panel.

Data collected at Visit 199 will be included in by-visit summaries and longitudinal modelling, if an assessment were scheduled at the mapped visit for Visit 199.

## Unscheduled assessments

Unscheduled assessments will be included in over period minimum/maximum, and in over period shift table, but will not be included in by-visit summary and longitudinal modelling.

## Model non-convergence

For all regression models, if the model fitting procedure does not converge, covariates could be removed from the model sequentially, as applicable, with the following order: visit-by-baseline interaction, stratum-by-BSBP interaction, stratum-by-baseline interaction, BSBP, baseline, region and stratum (ACEi, ARB, No RASi).

## 2.2 Analysis sets

The following analysis sets will be used for the statistical analyses.

- **Screened set (SCR)** – All patients who signed the informed consent for CLCZ696D2302. The SCR includes only unique screened patients, i.e., in the case of re-screened patients only the chronologically last screening data is counted.

- **Randomized set (RAN)** – All patients in the SCR who received a randomization number, regardless of receiving study drug.
- **Full analysis set (FAS)** – All randomized patients with the exception of those patients who have not been qualified for randomization and have not received study drug, but have been inadvertently randomized into the study, and the exception of those patients who have been inadvertently randomized within a wrong stratum (ACEi, ARB, No RASi) and have not received study drug. Further exclusions from the FAS may only be justified in exceptional circumstances (e.g., *serious* GCP violations). Following the intent-to-treat principle, patients will be analyzed according to the treatment to which they were assigned at randomization. Efficacy variables will be analyzed based on the FAS as the primary set.
- **Per protocol set (PPS)** – A subset of the FAS which will consist of the patients who do not have major deviations from the protocol procedures in the randomized treatment epoch. Major protocol deviations will be pre-specified prior to unblinding treatment codes for analyses. This supplemental efficacy set will be used to support the primary analysis results.
- **Safety set (SAF)** – All randomized patients who received at least one dose of study drug. Patients will be analyzed according to the treatment actually received. The SAF will be used for the analyses of safety variables. The treatment actually received will be considered identical to the randomized treatment if the patient has received at least one dose of the randomized treatment.

Patients without valid written informed consent will be excluded from all analysis sets. Further exclusions from the FAS are only justified in exceptional circumstances (e.g., site closed down for GCP reasons). The determination of which patients were excluded from the FAS is made in a blinded manner before the database lock.

Rules leading to exclusion from the analysis sets are given in [Appendix 5.2](#).

### 2.2.1 Subgroup of interest

[Table 2-3](#) specifies the subgroups to be used in sub-group analyses.

**Table 2-3 Subgroup specifications**

Subgroups	Source		
	Data Source	Variable	Visit/Time Point
Region			

 
• North America;
 
• Latin America (including Central America)
 
	Randomization	Region	Randomization

 
• Europe;
 
• Asia/Pacific and other
 
			
Stratum (ACEi, ARB, No RASi)			

 
• ACEi;
 
• ARB;
 
• No RASi;
 
	Randomization	Stratum	Randomization

Subgroups	Source		
	Data Source	Variable	Visit/Time Point
Age group (< 65 years, ≥ 65 years) 
 
< 65 years;
 
≥ 65 years;
 
	CRF page: Demography	Age	Screening
Age group (< 75 years, ≥ 75 years) 
 
< 75 years;
 
≥ 75 years;
 
	CRF page: Demography	Age	Screening
Sex 
 
Female;
 
Male;
 
	CRF page: Demography	Sex	Screening
Baseline NYHA class group 
 
Class I/II
 
Class III/IV
 
	CRF page: Signs and Symptoms of Heart Failure including New York Heart Association Classification	NYHA Classification	Randomization (Baseline)
Diabetes (history or HbA1c ≥ 6.5%)* 
 
Yes
 
No
 
	CRF page: Heart failure and Diabetes History Central laboratory result	Diabetes mellitus history HbA1c	Screening
LVEF group (≤ 60%, > 60%) 
 
≤ 60 %
 
> 60 %
 
	CRF page: Heart failure and Diabetes History	LVEF	Screening
Prior heart failure hospitalization 
 
Yes
 
No
 
	CRF page: Heart failure and Diabetes History	Prior heart failure hospitalization	Screening

NOTE: Baseline NYHA class is defined using the baseline criteria for efficacy variables (Section 2.1.1)

NOTE \*: Diabetes (history or HbA1c ≥ 6.5%) is defined as No if the patient has no history of diabetes mellitus and HbA1c at screening < 6.5%; Diabetes (history or HbA1c ≥ 6.5%) is defined as Yes if the patient has history of diabetes mellitus or HbA1c at screening ≥ 6.5%.

Table 2-4 summarizes the subgroup analyses in this study.

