	
The following secondary null hypotheses will be included in the testing strategy.
 
• H₃: LCZ696 is no better than the comparator in change from baseline in KCCQ clinical summary score (CSS) at Week 24 in the overall study population.• H₄: LCZ696 is no better than the comparator in NYHA change from baseline at Week 24 in the overall study population. 
Each null hypothesis is tested against the one-sided alternative that LCZ696 is better than the comparator in the corresponding variable. In order to control the family-wise type-I error rate at the one-sided 0.025 significance level, a sequentially rejective multiple testing procedure based on the graphical presentation (Bretz et al 2009) will be employed, whereby the testing procedure is graphically illustrated in Figure 9-1. Based on the above testing procedure, if applicable, H₁, H₂ and H₃ will be tested based on the corresponding MMRM models (Section 9.4.2, Section 9.5.1.1), and H₄ will be tested based on the longitudinal proportional cumulative odds model (Section 9.5.1.3).
 
If statistical significance had been established in the mean difference in change from baseline to Week 24 for KCCQ CSS, the following responders will be analyzed accordingly, based on the longitudinal binary logistic regression models (Section 9.5.1.1), to further illustrate the clinical relevance of the observed differences in terms of proportion of responders.
 
• KCCQ CSS improvement (defined by at least 5 points improvement);• KCCQ CSS deterioration (defined by at least 5 points deterioration); 
No multiplicity adjustment will be done for these supportive responder analyses (i.e., the tests for the responder analyses will be performed at nominal level of one-sided 0.025).

Key words	Heart failure with preserved ejection fraction, exercise capacity, symptoms, NT-proBNP, 6MWD, 6MWT, KCCQ, NYHA, SF-36

Amendment 2

Amendment rationale

The completed study CLCZ696B2314 (PARADIGM-HF) targeted patients with HF and reduced ejection fraction ($EF \leq 40\%$). Two ongoing studies (PARAGON and PARALLAX), and one completed phase 2 study (PARAMOUNT) in patients with HF and preserved ejection fraction include patients with $EF \geq 45\%$. Therefore, this amendment will expand the EF inclusion criteria from current $\geq 45\%$ to $>40\%$ in order to ensure that the LCZ696 clinical development program will cover the full EF spectrum.

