Due to the increasing importance of generating exercise capacity data in the HFpEF population, this amendment elevates change in six-minute walk distance (6MWD) to a primary endpoint. The primary analysis was selected to be performed in a sub-set of patients with baseline six-minute walk distance (B6MWD) ranging from 100 meters to 450 meters. Similar criteria was used in other HF studies ([Abraham et al 2002](#), [Abraham et al 2015](#), [Redfield et al 2015](#) and [Palau et al 2016](#)).

The amendment also includes a strategy for the multiplicity testing of the primary and secondary efficacy endpoints, as agreed with major Health Authorities.

An additional 300 patients will be enrolled to ensure that patients with LVEF $>40\%$ are represented in CLCZ696D2302 study population without jeopardizing or compromising any key study objective or assessment, which have previously been agreed upon with key external stakeholders.

Changes to the protocol

The main changes in this amendment are:

1. To expand the EF inclusion criteria from the current $\geq 45\%$ to $> 40\%$
2. To increase sample size from current 2,200 to 2,500 patients.
3. To elevate change in 6MWD as a primary endpoint in a subset of patients and remove it as a secondary endpoint
4. To include a testing strategy of the primary and secondary efficacy variables in the multiple testing procedure to control the family-wise Type-I error rate.
5. To provide clarifications, both on the patient profile and the study design; as well as, making editorial changes.

Changes to specific sections of the protocol are shown in the track changes version of the protocol using ~~strike through red font for deletions~~ and red underlined for insertions. A copy of this amended protocol will be sent to the Institutional Review Board (IRBs)/Independent Ethics Committee (IECs) and Health Authorities. In addition, if the changes herein affect the Informed Consent, sites are required to update and submit for approval of a revised Informed Consent that takes into account the changes described in this amended protocol.

Amendment 1

Amendment rationale

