Structural heart disease (LAE and LVH) is a key diagnostic criterion for HFpEF in the most recent guidelines (Ponikowski et al 2016). Left atrial (LA) size (an integrative measure of left ventricular diastolic pressure) is independently associated with an increased risk of morbidity and mortality (Zile et al 2011). Including echocardiographic evidence of structural heart disease consistent with HFpEF will help facilitate homogeneity of the study population. Both TOPCAT (Pitt et al 2014) and I-Preserve (Massie et al 2008) used an EF lower boundary threshold of 45%. This is also the threshold used in PARAGON-HF, an ongoing large outcomes study (4600 patients) comparing valsartan 160 mg bid to LCZ696 200 mg bid in HFpEF. Elevated NT-proBNP levels aid in the diagnosis of HFpEF. Current guidelines include NT-proBNP > 125 pg/mL as one of the criteria to be used for the diagnosis of HFpEF (Ponikowski et al 2016). In this symptoms study, we have chosen a threshold for NT-proBNP of 220 pg/mL which is consistent with prior guidelines (Paulus et al 2007) to increase the likelihood that patients' symptoms at baseline are related to HF rather than their comorbid conditions. NT-proBNP was the strongest independent predictor of mortality and subsequent HF hospitalizations in the I-PRESERVE study (Solomon et al 2007, Komajda et al 2011) and was used as an inclusion criterion in TOPCAT. Patients with baseline AF are required to have higher NT-proBNP levels, as AF is strongly associated with higher levels of NT-proBNP (McKelvie et al 2010). The number of patients with EF $< 45\%$ will be targeted to approximately 300 patients and the number of AF patients will be limited to approximately one-third in the current study (based on the Visit 1 electrocardiogram [ECG]) so that the proportion of patients with EF $< 45\%$ and AF in the study will be representative of the HFpEF population (Massie et al 2008, Steinberg et al 2012, West et al 2011, Tsuji et al 2017, Lund et al 2018).

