3.2.2 Rationale for the primary endpoints

The study has two primary endpoints: NT-proBNP and 6MWD.

NT-proBNP: One of the primary endpoints of this study is the change from baseline in NT-proBNP (in log scale) at Week 12. In a prior study in over 300 HFpEF patients, LCZ696 showed

a significantly greater reduction in NT-proBNP at Week 12 as compared to valsartan (Solomon et al 2012). Aggregate clinical data have demonstrated that NT-proBNP not only provides value for the diagnosis, and helps the management of patients with HF, but also predicts clinical outcome (mortality and morbidity). Studies suggest that NT-proBNP levels strongly correlate with adverse clinical outcomes in HF patients including death and hospital admission for chronic HF (Hartmann et al 2004, Hunt et al 2005, Masson et al 2008, McMurray et al 2014).

Across all stages of HF, elevated BNP/NT-proBNP concentration are the most robust prognostic predictor of mortality and cardiovascular events compared to other traditional outcome predictors (peak oxygen consumption, blood urea nitrogen (BUN), SBP and pulmonary capillary wedge pressure) with increasing BNP/NT-proBNP concentration predicting worse prognosis in a linear fashion (Sachdeva et al 2010).

In this short term study in patients with HF, change of NT-proBNP is considered an appropriate surrogate endpoint for clinical outcomes of HF. We will use this data to determine the treatment effect of LCZ696 compared to individualized medical therapy for comorbidities on the risk and clinical status of the population. In addition, the NT-proBNP data from this study can be used as a bridge to the PARAGON-HF study where NT-proBNP is also measured.

Six-minute walk distance (6MWD): The other primary endpoint is change from baseline in 6MWD which is derived from a simple, inexpensive, and reproducible test (6MWT) for the assessment of exercise capacity. It evaluates the global and integrated responses of all the systems involved during exercise including the pulmonary and cardiovascular systems. The 6MWD correlates well with results using formal treadmill exercise testing and has been shown to predict outcomes in patients with HF, particularly, in patients with more advanced HF (Pollentier et al 2010).

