### 2.5.5 Subgroup analyses

For each primary endpoint (Section 2.5.1), subgroup analyses will be performed utilizing the corresponding primary analysis model (Section 2.5.2), after adding the fixed-effect factors of subgroup variable and subgroup-variable-by-treatment interaction into the original model. The following subgroup variables (Section 2.2.1, Table 2-3) will be used for the subgroup analyses for both primary endpoints.

- Region
- Stratum (ACEi, ARB, No RASi)
- Age group (< 65 years,  $\geq$  65 years)
- Age group (< 75 years,  $\geq$  75 years)
- Sex
- Baseline NYHA class group
- Diabetes (history or HbA1c  $\geq$  6.5%)
- LVEF group ( $\leq$  60%, > 60%)
- Prior heart failure hospitalization

For changes from baseline in log(NT-proBNP), based on the subgroup analysis models, the estimates and the two-sided 95% confidence intervals will be provided for adjusted geometric means for ratio to baseline in NT-proBNP at Week 12 in both treatment groups (LCZ696 and IMT) within each subgroup, and for the ratio of the adjusted geometric means (LCZ696/IMT) at Week 12 within each subgroup; the p-value for the subgroup-variable-by-interaction will be provided for each subgroup variable.

For changes from baseline in 6MWD, based on the subgroup analysis models, the estimates and the two-sided 95% confidence intervals will be provided for the adjusted means for the change from baseline in 6MWD at Week 24 in both treatment groups (LCZ696 and IMT) within each subgroup, and for the adjusted mean difference (LCZ696 minus IMT) at Week 24 within each subgroup; the p-value for the subgroup-variable-by-interaction will be provided for each subgroup variable.

In addition, for each primary endpoint (Section 2.5.1), multivariate subgroup analyses will be performed utilizing the corresponding primary analysis model (Section 2.5.2), after adding the fixed-effect factors of all the following subgroup variables and subgroup-variable-by-treatment interactions into the original model. The p value for the global interaction test (null hypothesis: all interaction terms are equal to zero) will be presented, together with the p value for each interaction.

- Region
- Stratum (ACEi, ARB, No RASi)
- Age group (< 75 years, ≥ 75 years)
- Sex
- Baseline NYHA class group
- Diabetes (history or HbA1c ≥ 6.5%)
- LVEF group (≤ 60%, > 60%)
- Prior heart failure hospitalization

The FAS will be used for the above subgroup analyses.

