**Table 5-1 Protocol deviation criteria leading to exclusion from the analysis sets**

ID	Protocol Deviation Description	Excluding from Analysis Set				
		SCR	RAN	FAS	PPS	SAF
INCL01A	No study informed consent obtained	X	X	X	X	X

	Protocol Deviation	Excluding from Analysis Set		
INCL03A	Patient's qualifying LVEF <= 40% or the qualifying echo does not support LVEF >40%			X
INCL04	Heart failure symptoms not requiring diuretic treatment for at least 30 days prior to Visit 1			X
INCL05	NYHA Class I at Visit 1 or no heart failure symptoms at Visit 1			X
INCL08A	NT-proBNP at Visit 1 <= 220 pg/mL and no atrial fibrillation/atrial flutter (AF) on the Visit 1 ECG			X
INCL08B	NT-proBNP at Visit 1 <= 600 pg/mL and atrial fibrillation/atrial flutter (AF) on the Visit 1 ECG			X
INCL09	KCCQ clinical summary score >= 75 at Visit 1			X
EXCL08	Walking distance primarily limited by non-cardiac comorbid conditions			X
TRT03	Patient was randomized in error and no double-blind study medication was taken	X	X	X
TRT05	Patient was randomized within the wrong stratum and no double-blind study medication was taken	X	X	X
OTH01	Major GCP violation at site	X	X	
OTH02	Blind was broken accidentally at the site			X

Table 5-2 presents patient classification criteria including protocol deviation criteria and non-protocol-deviation criteria leading to exclusion from analysis sets.

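### Does the SAP need an LVEF subgroup cut at 45%, given that Amendment 2 opened entry to EF above 40%?

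*SAP*

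**What the plan says.** SAP Table 2-3 defines one LVEF variable, "LVEF group (≤ 60%, > 60"%). Table 2-4 and SAP 2.5.5 and 2.6.5 apply it to the primary, secondary and selected safety analyses. It also enters the multivariate subgroup model, which is fitted "after adding the fixed-effect factors of all the following subgroup variables and subgroup-variable-by-treatment interactions into the original model". Protocol 9.5.1.7 lists no LVEF subgroup. The spline analysis in SAP 2.5.4 models baseline walk distance and systolic pressure, not LVEF. Otherwise LVEF appears as a baseline summary (SAP 2.3.2) and as a per-protocol check, "qualifying LVEF <= 40% or the qualifying echo does not support LVEF >40"% (SAP Table 5-1). No planned output uses a 45% cut.

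On the widened entry range, the Amendment 2 rationale gives the reason as "in order to ensure that the LCZ696 clinical development program will cover the full EF spectrum", and continues: "An additional 300 patients will be enrolled to ensure that patients with LVEF" above 40% are represented. Protocol 3.2.1 says that the number with EF below 45% "will be targeted to approximately 300 patients", so that their share resembles that in the HFpEF population. On the 45% figure, the same section says "This is also the threshold used in PARAGON-HF, an ongoing large outcomes study". Protocol 3.2.2 adds that "the NT-proBNP data from this study can be used as a bridge to the PARAGON-HF study".

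**The concern.** The protocol itself points to 45%. It was the entry limit before Amendment 2, it is PARAGON-HF's limit, and it marks off the roughly 300 patients the amendment was meant to bring in. The SAP then splits LVEF at 60%, for which neither document gives a reason, and so pools everyone below 45% with everyone from 45% to 60%. A reader could conclude that the plan enrols a new population and never looks at it, and that it offers a bridge to PARAGON-HF without an estimate in the shared EF range. A 45% cut made after unblinding would be post hoc. If the effect differed in the new patients, the overall estimate might also misstate the effect in the range PARAGON-HF covers.

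**Working it through.** **Inputs.** From SAP section 3: N = 2500; log NT-proBNP SD 0.81 with 10% dropout; 6MWD SD 120 m with 10% dropout and 88% in the 100 to 450 m range; KCCQ CSS SD 15.52 with 5% dropout. Allocation is 1:1. Assumed: exactly 300 patients with EF <45% (the protocol gives an approximate target), evenly split between arms, with the same SDs, dropout and 88% share in both EF ranges.

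**The plan's own figures** (normal approximation, SE = SD × √(2/n per arm)):
- NT-proBNP: n = 2500 × 0.90 / 2 = 1125 per arm; an 11% reduction is −ln 0.89 = 0.1165; power at one-sided 0.0225 is 92.0% (stated 92%).
- 6MWD: n = 2500 × 0.90 × 0.88 / 2 = 990; 22 m at one-sided 0.0025 gives 89.8% (stated 90%).
- KCCQ CSS: n = 2500 × 0.95 / 2 = 1187.5; 2 points at one-sided 0.0225 gives 87.2% (stated 87%).

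**Would an EF ≥45% estimate differ from the overall one?** EF <45% is 300/2500 = 12% of patients. If the effect is e in EF ≥45% and zero below, the overall effect is about 0.88e, a gap of 0.12e. If the effect below 45% is 2e, the gap is the same size in the other direction.

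| Endpoint | e | Gap 0.12e | 95% half-width, EF ≥45% | Gap / half-width |
|---|---|---|---|---|
| log NT-proBNP | 0.2744 (24%) | 0.033 | 1.96 × 0.81 × √(2/990) = 0.071 | 46% |
| log NT-proBNP | 0.1165 (11%) | 0.014 | 0.071 | 20% |
| 6MWD | 22 m | 2.64 m | 1.96 × 120 × √(2/871.2) = 11.3 m | 23% |
| 6MWD | 30 m | 3.6 m | 11.3 m | 32% |
| KCCQ CSS | 2 points | 0.24 | 1.96 × 15.52 × √(2/1045) = 1.33 | 18% |
| KCCQ CSS | 3 points | 0.36 | 1.33 | 27% |

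On the ratio scale, a 24% NT-proBNP reduction in EF ≥45% would appear as 1 − exp(0.88 × ln 0.76) = 21.5% overall, and 11% as 9.7%.

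**What would an EF <45% row show?** Power is at nominal one-sided 0.025.
- NT-proBNP: 135 per arm; SE = 0.81 × √(2/135) = 0.0986; interval ×/÷ exp(1.96 × 0.0986) = 1.21; power 22% for an 11% reduction and 79% for 24%. An observed ratio of 0.89 would carry an interval of 0.73 to 1.08.
- 6MWD: 300 × 0.90 × 0.88 / 2 = 118.8 per arm; ±30.5 m; power 29% for 22 m.
- KCCQ CSS: 142.5 per arm; ±3.6 points; power 19% for 2 points.
- NT-proBNP interaction across 45%: SE = √(0.0986² + 0.0364²) = 0.1051; power 20% (zero versus 11%) to 74% (zero versus 24%).

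**What the text commits to.** Protocol 3.2.1 targets the EF <45% number for representativeness, and the same sentence limits AF to about one-third for the same reason. AF has no efficacy subgroup in Table 2-3 either, so in this plan an enrolment target does not imply a subgroup estimate. The Amendment 2 aim concerns coverage across the development programme. The bridge sentence in 3.2.2 is permissive and rests on NT-proBNP being measured in both studies. No bridging analysis is defined, and one would need PARAGON-HF data and could set its own EF restriction.

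**The case for a change.** The best case for a 45% cut rests on EF ≥45%, not on the small group below. That estimate would have about 990 evaluable patients per arm for NT-proBNP and 89% nominal power for an 11% reduction. It matches both the pre-amendment entry range and PARAGON-HF's. The SAP was revised for Amendment 2 and again later, each time before database lock, and LVEF is already collected, so the rows would cost little and would be pre-specified. The 60% split cannot stand in for them: if 60 to 90% of patients have EF ≤60% (an assumption, since neither document gives a distribution), those below 45% make up only 13 to 20% of that group. At the upper design effect, NT-proBNP power in EF <45% would reach 79%.

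The facts in this stand: no planned output isolates either range, and a later cut would be post hoc. It does not follow that the plan is deficient. The EF ≥45% group is 88% of the trial, so its estimate would largely repeat the overall one. The EF <45% row could settle little at the lower design effects. It would also rest on local echoes and on randomization stratified by prior RASi use and region, not EF (Protocol 5.3). Subgroup analyses lie outside the H1 to H4 testing graph in any case.

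**Conclusion.** The concern does not hold. The observation is correct: the only LVEF treatment-effect subgroup is split at 60%. But no rule, number, objective, alpha level or primary conclusion in the documents depends on a 45% split, and the stated purpose of enrolling patients below 45% is met by including them in the analysed population. With no effect below 45%, or twice the effect, the overall NT-proBNP log ratio stays within 0.033 of the EF ≥45% value, less than half of that subgroup's 95% half-width of 0.071. For 6MWD and KCCQ CSS the gap is at most about a third of the half-width. These sizes rest on roughly 300 patients below 45%, balanced arms and common SDs. A clearly larger share, or an effect below 45% that runs in the opposite direction, would widen the gap. A 45% row would be a supportive addition some readers would welcome, and leaving it out is a choice the plan may make.
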